## APPENDIX B – FORM 1 (REGISTRATION AND ELIGIBILITY)

SUBJECT Initials: \_\_\_\_\_ MR# \_\_\_\_\_ DOB: \_\_\_\_\_

CENTER: \_\_\_\_\_ Date: \_\_\_\_\_

Treating Physician: \_\_\_\_\_

**“A Phase I/II study of lenalidomide maintenance after autologous stem cell transplant for elderly patients with Acute Myeloid Leukemia (AML).”**

Inclusion Criteria:	YES	NO
The answers to the following questions must be YES in order for the patient to be eligible.		
3.1.1. Patient has a confirmed diagnosis of non-M3 AML. Antecedent MDS is acceptable.		
3.1.2. Post autologous Stem Cell Transplant Bone marrow biopsy core that is consistent with morphologic remission.		
3.1.3. Age between 60 and 80 years old.		
3.1.4. Patient received induction and consolidation chemotherapy, and autologous stem cell transplant for AML.		
3.1.5. Life expectancy of greater than 12 months.		
3.1.6. Karnofsky Performance Status 70 or greater (see Appendix A)		
3.1.7. Patients have normal organ and marrow function as defined below: - Leukocytes $\geq 2,000/\text{mL}$ - Absolute neutrophil count $\geq 1,000/\text{mL}$ - Platelets $\geq 75,000/\text{mL}$ - Total bilirubin $\leq 4 \times$ institutional upper limit of normal unless 2nd to Gilbert's disease - AST(SGOT) and ALT(SGPT) $\leq 4 \times$ institutional upper limit of normal - Creatinine $< 1.5 \times$ institutional upper limit of normal OR creatinine clearance $\geq 30 \text{ mL/min/1.73 m}^2$ for patients with creatinine levels above institutional normal.		
3.1.8 Able to take aspirin, or warfarin, or low molecular weight heparin as prophylactic anticoagulation.		
3.1.9. Ability to understand and the willingness to sign a written informed consent document.		
3.1.10 Patient will be registered into the mandatory RevAssist® program and be willing and able to comply with the requirement of RevAssist®.		

Exclusion Criteria:	YES	NO
The answers to the following questions must be NO in order for the patient to be eligible.		
3.2.1. Patient received chemotherapy or radiotherapy within 2 weeks prior to entering the study or has not recovered from adverse events due to agents administered more than 4 weeks earlier.		
3.2.2 Patient received another investigational agent after post autologous stem cell transplant.		
3.2.3 Patient will be receiving another investigational product during the study.		
3.2.4 Patient who is growth factor or transfusion dependent.		
3.2.5 Patient has CNS leukemia.		
3.2.6 Patient has a history of allergic reactions attributed to thalidomide or lenalidomide.		
3.2.7 Patient has a history of erythema nodosum, characterized by a desquamating rash while taking thalidomide or similar drugs.		
3.2.8 History of metastatic malignancy.		
3.2.9 Presence of uncontrolled illness including, but not limited to ongoing or active infection, unstable angina pectoris, cardiac arrhythmia, or psychiatric illness/social situations that would limit compliance with study requirements. Patients must not have suffered recent (< 6 months) myocardial infarction, unstable angina, uncontrolled hypertension, or difficult to control cardiac arrhythmias.		
3.2.10 Evidence of uncontrolled Congestive Heart Failure (CHF).		
3.2.11 Active Hepatitis B as defined by Hepatitis B surface antigen positivity, unless able to start dual anti-HepB therapy, or already on dual anti-HepB therapy		
3.2.12 Patient is positive for Hepatitis B core antibody, but negative for the hepatitis B surface antigen, and is on lamivudine 100 mg daily until at least 3 months post-transplant		
3.2.13 Patient is positive for HIV or HTLV-1.		
3.2.14 Patient is woman of childbearing potential (defined as a sexually mature woman who has not undergone a hysterectomy or who has had menses at any time in the preceding 24 consecutive months).		
3.2.15 Patient is a man who agreed not to father a child and agreed to use a latex condom during any sexual contact with women of childbearing potential while taking lenalidomide and for 4 weeks after therapy is stopped, even if they have undergone a successful vasectomy.		

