#### **3.2 Exclusion Criteria**

- 3.2.1. Patient received chemotherapy or radiotherapy within 2 weeks prior to entering the study or has not recovered from adverse events due to agents administered more than 4 weeks earlier.
- 3.2.2 Patient received another investigational agent after post autologous stem cell transplant.
- 3.2.3 Patient who will be receiving another investigational product during the study.

- 3.2.4 Patient who is growth factor or transfusion dependent.
- 3.2.5 Patient has CNS leukemia.
- 3.2.6 History of allergic reactions attributed to thalidomide or lenalidomide.
- 3.2.7 History of erythema nodosum, characterized by a desquamating rash while taking thalidomide or similar drugs.
- 3.2.8 Prior history of metastatic malignancy.
- 3.2.9 Uncontrolled illness including, but not limited to ongoing or active infection, unstable angina pectoris, cardiac arrhythmia, or psychiatric illness/social situations that would limit compliance with study requirements. Patients must not have suffered recent (< 6 months) myocardial infarction, unstable angina, uncontrolled hypertension, or difficult to control cardiac arrhythmias.
- 3.2.10 Evidence of uncontrolled Congestive Heart Failure (CHF).
- 3.2.11 Active Hepatitis B as defined by Hepatitis B surface antigen positivity, unless able to start dual anti-HepB therapy, or already on dual anti-HepB therapy
- 3.2.12 Patients who are positive for Hepatitis B core antibody, but negative for the hepatitis B surface antigen, should be on lamivudine 100 mg daily until at least 3 months post-transplant
- 3.2.13 Patient is positive for HIV or HTLV-1.
- 3.2.14 Women of childbearing potential (defined as a sexually mature woman who has not undergone a hysterectomy or who has had menses at any time in the preceding 24 consecutive months).
- 3.2.15 Men who did not agree not to father a child and who refused to use a latex condom during any sexual contact with women of childbearing potential while taking lenalidomide and for 4 weeks after therapy is stopped, even if they have undergone a successful vasectomy.

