### 3.3 Inclusion of Women and Minorities

Both men and women and members of all races and ethnic groups are eligible for this trial.

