**Montefiore Medical Center-Moses Division**  
Department of Oncology, [name]  
[name]  
[name]  
[contact] or [contact]  
[contact] or [contact]

Coordinator: [name]  
Email: [[contact]](mailto:[contact])

Eligible patients will be entered on study centrally at the Montefiore-Einstein Cancer Center Coordinating Center by the Study Coordinator. All sites should call the Study Coordinator [name]; [contact] to verify eligibility. The required forms (eligibility and registration form; form 1) can be found in the Appendix (Appendix B).

Following registration, patients should begin protocol treatment within 96 hours. Issues that would cause treatment delays should be discussed with the Principal Investigator (PI). If a patient does not receive protocol therapy following registration, the patient's registration on the study may be canceled. The Study Coordinator should be notified of cancellations as soon as possible.

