#### 4.2 Registration Process

To register a patient, the following documents should be completed by the research nurse or data manager and faxed or e-mailed to the Study Coordinator at the Montefiore-Einstein Cancer Center Coordinating Center [name]; [contact], [contact] or email: [[contact]](mailto:[contact])

- Form 1 (Appendix B)
- Copy of required laboratory tests and procedures
- Signed patient consent form
- HIPAA authorization form

The research nurse or data manager at the participating site will then call the Study Coordinator at the Montefiore-Einstein Cancer Center Coordinating Center [name], [contact], [contact] or email: [[contact]](mailto:[contact]) to verify eligibility. To complete the registration process, the Coordinator will - after discussion with the PI, [name]:

[figure not shown]
- Assign a patient study number
- Register the patient on the study
- Fax or e-mail the patient study number to the participating site
- Call the research nurse or data manager at the participating site and verbally confirm registration.

Once patients are found eligible for the study, they will be registered with the Montefiore-Einstein Cancer Center Coordinating Center. A patient number will be assigned, and a copy of appendix B including the patient number will be faxed back to the participating center/investigator.

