#### ***Male Patients:***

Must agree to practice complete abstinence or agree to use a condom during sexual contact with pregnant females or females of childbearing potential throughout the entire duration of lenalidomide treatment, during dose interruptions and for at least 28 days following lenalidomide discontinuation, even if he has undergone a successful vasectomy.

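### Form 1 item 3.2.15 is worded the wrong way round: a man who agrees to contraception is recorded as ineligible, and a man who refuses passes that item

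*Combined protocol and SAP*

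**What the plan says.** Section 4.1 makes Form 1 the required eligibility and registration form. Section 4.2 puts it first among the registration papers: "To register a patient, the following documents should be completed by the research nurse or data manager". The coordinator verifies eligibility and registers the patient after discussion with the PI.

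The exclusion block of Form 1 is governed by one instruction: "The answers to the following questions must be NO in order for the patient to be eligible". Item 3.2.15 in that block begins "Patient is a man who agreed not to father a child and agreed to use a latex condom during any sexual contact" and continues with the partners and period covered.

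The criterion it is meant to reproduce, Section 3.2.15, excludes "Men who did not agree not to father a child and who refused to use a latex condom during any sexual contact". The partners covered are women of childbearing potential, and the period is treatment plus 4 weeks. Appendix F states the rule for male patients positively: "Must agree to practice complete abstinence or agree to use a condom during sexual contact with pregnant females or females of childbearing potential". It applies throughout treatment, "during dose interruptions and for at least 28 days following lenalidomide discontinuation, even if he has undergone a successful vasectomy".

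On hepatitis B, Section 3.2.12 says that core-antibody-positive, surface-antigen-negative patients should take lamivudine until at least 3 months after transplant. Form item 3.2.12 turns this into a statement that the patient has that serology and is taking lamivudine, again to be answered NO.

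**The concern.** An exclusion checklist works only if each item describes the state that disqualifies. Item 3.2.15 describes the state that qualifies, so following the form exactly gives the wrong answer for both kinds of man: the one who agrees and the one who refuses.

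The condition is a safety criterion for a drug whose human teratogenicity the protocol says cannot be ruled out. Women of childbearing potential are already excluded by 3.2.14, so contraception by male participants is the main pregnancy-related condition left for eligibility screening to record. With the item as it stands, each compliant man must either be shown on file as meeting an exclusion, so that his enrolment looks like an eligibility violation, or have the item answered against its wording. Neither record shows that he gave the undertakings.

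**Working it through.** No figure in the plan depends on this point. The check takes each form item with the instruction that it must be answered NO, and compares the result with Section 3.2 and Appendix F.

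**Item 3.2.15**

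| Candidate | Truthful answer on Form 1 | Result on the form | Result under Section 3.2.15 |
|---|---|---|---|
| Man, gives both undertakings | YES | Ineligible | Eligible |
| Man, gives neither | NO | Passes the item | Excluded |
| Man, gives only one | NO | Passes the item | Depends on how 'and' is read |
| Woman | NO | Passes the item | Not addressed |

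The first two rows are unambiguous, and both are wrong on the form. Appendix F settles the intended direction, because it requires agreement.

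The third row exposes a smaller weakness in Section 3.2.15 itself. Its two failures are joined by 'and'. Read literally, a man who promises not to father a child but refuses condoms is not excluded, although Appendix F would not accept him unless he were abstinent. Joining the failures with 'or' closes that gap.

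**Coverage against Appendix F**

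- *Period after treatment:* 4 weeks in Section 3.2.15 and on the form, 28 days in Appendix F. 4 × 7 = 28, so they agree.
- *Dose interruptions:* named in Appendix F, absent from Section 3.2.15 and the form. Section 5.1 allows holds of up to 8 weeks. Even if a hold counted as stopping therapy, the 4-week tail would leave up to 8 − 4 = 4 weeks uncovered. This is a real gap in the criterion's wording, although Appendix F already imposes the duty.

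**Item 3.2.12** (core-antibody positive, surface-antigen negative)

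| Candidate | Truthful answer on Form 1 | Result on the form | Section 3.2.12 |
|---|---|---|---|
| On lamivudine | YES | Ineligible | The recommended state |
| Not on lamivudine | NO | Passes the item | Should be on it until at least 3 months post-transplant |

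Screening runs from post-transplant day 15 to day 100 (Section 6.1). Taking 3 months as about 90 days, roughly 75 of those 85 days fall in the period when lamivudine is recommended. Adjacent item 3.2.11 takes the opposite approach and keeps treated patients eligible.

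**Extent.** Comparing all 15 exclusion items on Form 1 with Section 3.2, 13 keep their meaning (3.2.1 to 3.2.11, 3.2.13, 3.2.14) and 2 do not (3.2.12, 3.2.15); 13 + 2 = 15.

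**The case against.** The strongest reply is that this is a copying slip in a checklist. Section 3.2.15 and Appendix F both have the right direction, and site staff will understand what is meant. That is fair as a description of origin and probably of effect. It does not make the form harmless: the form is the operative registration document, it is completed by a research nurse or data manager, and Section 10.2 foresees adding sites whose staff did not write it.

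Four stronger readings are tempting, and the documents do not support them.

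- *The form would put men who refuse contraception on treatment.* Such a man passes one item only. He must still be willing to comply with RevAssist (3.1.10), Appendix F requires his agreement before lenalidomide is started, and registration follows discussion with the PI.
- *The trial is closed to compliant men, so accrual suffers.* Only a literal reading of the form gives that result, and Section 3.3 states the opposite intent: "Both men and women and members of all races and ethnic groups are eligible for this trial".
- *Section 3.2.15 leaves out abstinence and pregnant partners.* An abstinent man can give the condom undertaking, since it binds only when there is sexual contact. A pregnant partner would ordinarily meet the definition of childbearing potential in 3.2.14. Only dose interruptions are clearly missing.
- *Form item 3.2.12 reverses an exclusion.* Section 3.2.12 states no exclusion. It is a management instruction placed in an exclusion list, and the form turned it into a disqualifying condition.

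**Conclusion.** The point holds for item 3.2.15. Applied as written, Form 1 gives the wrong result on that item both for men who give the two undertakings and for men who give neither, contrary to Section 3.2.15 and Appendix F. It bears on every male candidate; the documents do not say how many there will be. The other safeguards make practical harm likely to be small, and there is no effect on sample size or analysis. What remains is an operative safety criterion that gives a wrong record and costs almost nothing to correct, so it should be fixed.

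Item 3.2.12 is a secondary note: the form penalises recommended treatment, for a number of patients that is also not given.

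The conclusion assumes that the items are answered truthfully as worded and that nothing after item 3.2.15 on the form changes how it is to be answered.

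**What to change.** Reword form item 3.2.15 so that YES means failure. For example: *Patient is a man who will not undertake to avoid fathering a child, or who refuses to use a latex condom whenever he has sexual contact with a woman of childbearing potential, for as long as he is on lenalidomide (dose interruptions included) and for 4 weeks after stopping, vasectomy or not.* This keeps both undertakings and the latex requirement. Use the same 'or' wording in Section 3.2.15. That change is deliberate: it makes explicit that failing either undertaking excludes, which the present 'and' leaves open.

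For 3.2.12, take the item out of the YES/NO exclusion list and keep it as a management instruction, or reword it so that being on lamivudine does not disqualify. Neither route should introduce an exclusion that Section 3.2.12 does not state.

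Check how both items were answered on forms already completed, and annotate any entry where the answer and the patient's actual status disagree. The cost is a minor amendment, a reissued Form 1 and that check.

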## APPENDIX C

### HANDLING AND SHIPPING OF BONE MARROW SPECIMENS:

#### HANDLING AND SHIPPING OF BONE MARROW AND OTHER SPECIMENS FOR CORRELATIVE STUDIES:

All specimens for correlative studies must be labeled with the patient's code number, which will be assigned by the Data Management Office, and should not bare the patient's identity. The specimens must be kept at room temperature and sent by fedex to:

[name]  
Albert Einstein College of Medicine,  
[name]  
[name]  
[contact]  
[contact]  
[[contact]](mailto:[contact])

**Bone Marrow Aspirate:** 10cc of heparinized marrow aspirate will be required. We will perform flow cytometry and genome wide sequencing from these samples. RNA and DNA from patient bone marrow specimens at baseline will be sequenced to correlate expression patterns and mutational patterns with response. Three unstained slides containing bone marrow aspirate will be required for further studies

1. Prepare a conical tube for the bone marrow specimen by adding 0.5 ml of preservative-free sodium heparin (400 U/ml stock solution) to a 50 ml polypropylene conical tube.
2. Collect **10 cc, if possible** of bone marrow using a needle/syringe with preferably citrate or if citrate is not available, then with heparin, and transfer it to the tube containing heparin.
3. Add RPMI-1640, at 1:1 ratio (i.e.; 20 ml bone marrow plus 20 ml RPMI-1640).
4. Invert the tube to mix thoroughly and minimize clotting potential
5. Screw the cap on the tube, and tightly wrap the lower edge of the cap with parafilm.

**Peripheral Blood:** If the bone marrow aspirate cannot be obtained then we will require 3 green top tubes, with 8 cc of blood each. Mononuclear cells from patient's peripheral blood will be purified by Ficoll-Hypaque sedimentation and these cells used for flow cytometry and sorting. These samples will also be used for interphase FISH studies (if abnormal cytogenetics found at diagnosis). Cells will be frozen for future RNA extraction to perform gene expression studies.

**Buccal swabs:** Buccal swabs with brushes will be done at baseline and stored in RNA later solution. RNA/DNA will be isolated from these samples and compared to bone marrow samples to determine somatic mutations in AML stem cells.

**Banking of Samples:** Peripheral blood, bone marrow, cell lysates, and cell products obtained from the previously mentioned samples will be stored for subsequent research related to this project.

6. \* Please page or call [name] ([contact]) to notify him that a shipment has been sent and for any questions. Sodium heparin (400 U/ml stock solution) to a 50 ml polypropylene conical tube.
7. Collect **10 cc, if possible** of bone marrow using a needle/syringe with preferably citrate or if citrate is not available, then with heparin, and transfer it to the tube containing heparin.
8. Add RPMI-1640, at 1:1 ratio (i.e.; 20 ml bone marrow plus 20 ml RPMI-1640).
9. Invert the tube to mix thoroughly and minimize clotting potential
10. Screw the cap on the tube, and tightly wrap the lower edge of the cap with parafilm.

## **Appendix D –Required Laboratory Parameters**

### **Complete Blood Count (CBC) with differential:**

White Blood Cells (WBC) count  
Red Blood Cells (RBC) count  
Hemoglobin  
Platelet count  
Neutrophil (%)  
Lymphocyte (%)  
Monocyte (%)  
Eosinophil (%)  
Basophil (%)  
Absolute Neutrophil count  
Absolute Lymphocyte count

### **Biochemistries:**

Sodium  
Potassium  
Chloride  
CO2  
Glucose  
Urea Nitrogen  
Calcium  
Creatinine  
Albumin  
Bilirubin (total)  
Bilirubin (direct)  
Alkaline Phosphatase  
SGOT  
SGPT  
Total Protein

*Clinical significant lab results must be graded and recorded in Adverse Event Page.*

**Appendix E – Cockcroft-Gault estimation of CrCl:**

Cockcroft-Gault estimation of creatinine clearance (CrCl):

(Cockcroft, 1976; Luke 1990)

$$\text{CrCl (mL/min)} = \frac{(140 - \text{age}) \times (\text{weight, kg})}{72 \times (\text{serum creatinine, mg/dL})}$$

**(Males)**

$$\text{CrCl (mL/min)} = \frac{(140 - \text{age}) \times (\text{weight, kg})}{72 \times (\text{serum creatinine, mg/dL})} \times 0.85$$

**(Females)**

## **Appendix F: Risks of Fetal Exposure, Pregnancy Testing Guidelines, Acceptable Birth Control Methods and Precautions.**

### **Risks Associated with Pregnancy**

The use of lenalidomide in pregnant females and nursing mothers has not been studied nor has the effect of the lenalidomide on human eggs and sperm. Lenalidomide is structurally related to thalidomide. Thalidomide is a known human teratogenic active substance that causes severe life-threatening birth defects. An embryo-fetal development study in animals indicates that lenalidomide produced malformations in the offspring of female monkeys who received the drug during pregnancy. The teratogenic effect of lenalidomide in humans cannot be ruled out. Therefore, a risk minimization plan to prevent pregnancy must be observed.

All study participants must be registered into the mandatory RevAssist® program, and be willing and able to comply with the requirements of RevAssist®. Criteria for females of childbearing potential (FCBP) This protocol defines a female of childbearing potential as a sexually mature female who:

- 1) has not undergone a hysterectomy or bilateral oophorectomy or
- 2) has not been naturally postmenopausal for at least 24 consecutive months (i.e., has had menses at any time in the preceding 24 consecutive months).

### **Contraception**

Females of childbearing potential (FCBP) enrolled in this protocol must agree to use two reliable forms of contraception simultaneously or to practice complete abstinence from heterosexual intercourse during the following time periods related to this study:

- 1) for at least 28 days before starting lenalidomide;
- 2) throughout the entire duration of lenalidomide treatment;
- 3) during dose interruptions; and
- 4) for at least 28 days after lenalidomide discontinuation.

The two methods of reliable contraception must include one highly effective method and one additional effective (barrier) method. FCBP must be referred to a qualified provider of contraceptive methods if needed. The following are examples of highly effective and additional effective methods of contraception:

- Highly effective methods:
  - Intrauterine device (IUD)
  - Hormonal (birth control pills, injections, implants)

- Tubal ligation
- Partner's vasectomy
  
- Additional effective methods:
  - Male condom
  - Diaphragm
  - Cervical Cap

Implants and levonorgestrel-releasing intrauterine systems are associated with an increased risk of infection at the time of insertion and irregular vaginal bleeding. Prophylactic antibiotics should be considered particularly in patients with neutropenia.

